2.3 Cetuximab

Cetuximab (Erbix[®], C-225) is a chimerized monoclonal IgG₁ subclass antibody with binding affinity to the epidermal growth factor receptor (EGFR) that exceeds the natural ligand epidermal growth factor (EGF). Cetuximab effectively blocks binding of EGF and transforming growth factor alpha (TGF- α) to EGFR and prevents ligand-induced activation, stimulates EGFR internalization, and effectively removes EGFR from the cell surface. Cetuximab is FDA approved for the treatment of head and neck cancers in combination with radiation and in the palliative setting typically with chemotherapy.

Several clinical studies have demonstrated the safety and efficacy of cetuximab in the treatment of HNSCC. Vermorken et al, treated 103 patients with incurable stage III/IV, platinum refractory HNSCC with single agent cetuximab (at 400 mg/m² initial dose and 250 mg/m² weekly subsequently)(*Vermorken, Trigo et al. 2007*). The objective response rate (ORR) in this population was 14%, median time to progression was 2.3 months and median overall survival (OS) was 5.9 months. The treatment was well tolerated.

In another trial 117 patients with metastatic or recurrent HNSCC were randomized between cetuximab plus cisplatin (100 mg/m² every 28 days) or cisplatin plus placebo. The addition of cetuximab to cisplatin improved ORR (26% vs. 10%), median PFS (4.2 months vs. 2.7 months), and median OS (9.2 months vs. 8.0 months) versus control. Cetuximab therapy was associated with increases in the risk of neutropenia, acneform rash, and dyspnea, but the treatment was generally well tolerated.

On the basis of this trial as well as other reports including combinations with chemotherapy and radiation in the pre-clinical and clinical setting two pivotal phase III studies were started. The first phase III trial enrolled 424 patients with locoregionally advanced HNSCC – randomization between cetuximab + radiotherapy (RT) versus radiation alone. Median progression free survival (primary endpoint) in the cetuximab/RT arm was 17.1 months, compared to 12.4 months in the RT alone

arm (= overall survival of 49 months versus 29.3 months. Both arms were reported to comparable RT related toxicities. The primary observed adverse event in this trial attributed to cetuximab was an acneform rash in 17% in the cetuximab/RT group and only 1% in the RT alone arm.

In 2008, results from the landmark phase III EXTREME trial (*Vermorken, Mesia et al. 2008*), comparing cetuximab in combination with either cisplatin plus 5-fluorouracil (5-FU) or carboplatin plus 5-FU with combinations of cisplatin/5-FU or carboplatin/5-FU alone were reported. Results indicated a statistically significant survival benefit associated with adding cetuximab to these regimens.

Based on trials using cetuximab (420 patients receiving cetuximab monotherapy or 354 patients receiving cetuximab + chemotherapy (patients with metastatic colorectal cancer)) cetuximab was well tolerated. The most **serious adverse reactions** associated with cetuximab were: Infusion reaction (3%); Dermatologic toxicity (1%); Interstitial lung disease (0.4%); Fever (5%); Sepsis (3%); Kidney failure (2%); Pulmonary embolus (1%); Dehydration (5%) in patients receiving cetuximab plus irinotecan, 2% in patients receiving cetuximab monotherapy; Diarrhea (6%) in patients receiving cetuximab plus irinotecan, 0% in patients receiving cetuximab monotherapy. 17 (4%) patients receiving cetuximab monotherapy discontinued treatment primarily because of adverse events. The most common adverse events seen in 420 patients receiving cetuximab monotherapy were acneform rash (90%), asthenia/malaise (48%), nausea (29%), fever (27%), constipation (26%), abdominal pain (26%), headache (26%), and diarrhea (25%). The most common adverse events seen in 354 patients receiving cetuximab plus irinotecan were acneform rash (88%), asthenia/malaise (73%), diarrhea (72%), nausea (55%), abdominal pain (45%), and vomiting (41%).

Cetuximab is currently Food and Drug Administration (FDA)- approved for use in combination with radiotherapy in the treatment of locally or regionally advanced HNSCC, as well as in the recurrent/ metastatic setting as a single agent, or in combination with cytotoxic chemotherapy.

2.4 Rationale

EGFR is expressed at very high levels in >90% of Head and Neck cancers (HNC; >NSCLC) and treatment with cetuximab (alone or in combination with chemotherapy or radiation) is now considered a standard of care. Nevertheless the response rate to EGFR inhibitors (cetuximab response rate = 13%, 40-50% stable disease) and median progression free survival of 70 days (*Vermorken et al, JCO, 2007*) remain disappointing. While treatment benefit is generally considered to be comparable to cytotoxic therapies with lower toxicity, the potential of EGFR as a therapeutic target in this highly EGFR expressing disease has not been fully exploited. Clinically treatment for recurrent/metastatic disease is either given in combination with chemotherapy (EXTREME) or after initial cytotoxic chemotherapy.

In our translational and preclinical work we demonstrated the following:

Eighty-four percent of the HNC samples showed c-MET overexpression (>NSCLC), and 18 of 20 HNC cell lines (90%) expressed c-MET. HGF overexpression was present in 45% of HNC. c-MET inhibition with SU11274/PF-2341066 abrogated c-MET signaling, cell viability, motility/migration in vitro, and tumor angiogenesis in vivo. Increased c-MET gene copy number was present with >10 copies in 3 of 23 (13%) tumor tissues. A greater-than-additive inhibition of cell growth was observed when combining a c-MET inhibitor with an EGFR inhibitor and synergy was mediated via erbB3 signaling. Finally we identified single nucleotide variants/mutations in the semaphorin (T230M/E168D/N375S), juxtamembrane (T1010I/R988C), and tyrosine kinase (T1275I/V1333I) domains (incidence: 13.5%) although functional contribution of these variants will require further study.

We demonstrated that c-MET is functionally important in HNC with prominent overexpression, and increased gene copy number, in the vast majority of HNC. c-MET inhibition abrogated c-MET functions, including proliferation, migration/motility, and angiogenesis. We concluded that c-MET is a promising, novel target for HNC and combination approaches with EGFR inhibitors should be explored.

The importance of c-MET in general for head and neck cancers and a relationship to EGFR signaling is well supported by corroborative literature: Knowles et al demonstrated the importance of HGF and c-MET for HNC independently (Knowles, et al Clinical Cancer Research 2009). Particular emphasis was put on the tumor fibroblast HGF production. Furthermore recent data from the Univ. of Pittsburgh (California Consortium) show strong synergy of c-MET with EGFR inhibition, and extensive crosstalk between the two receptors (Xu et al, Clinical Cancer Research, 2011).

Both EGFR and c-MET signal downstream via the common signaling adaptor/receptor erbB3, as demonstrated for NSCLC previously and confirmed for HNC (Seiwert et al, Cancer Research 2009). Preclinical co-targeting of EGFR and MET revealed strong synergy in HNC (Seiwert et al, 2009, Cancer Research; Xu et al, 2011, Clinical Cancer Research). Furthermore two phase II randomized studies in NSCLC have yielded positive results suggesting that c-MET inhibition can augment the efficacy of EGFR inhibition and improve PFS in biomarker defined patient populations. EGFR and MET signaling are overlapping and it is well established that one can compensate for the other and joint inhibition provides benefit/synergy. It is crucial to identify the correct biologic subgroup/s that benefit most. Our preclinical work as well as NSCLC lung cancer data suggest that increased c-MET copy number and c-MET expression are the most likely candidate predictive biomarkers also for HNC.

Based on these preclinical findings we now propose to study the EGFR inhibitor cetuximab and the c-MET inhibitor ARQ 197 (tivantinib) in combination.

2.5 Correlative Studies Background

See above for preclinical rationale. Clinically the rationale is largely supported by prior experiences with ARQ 197 (tivantinib) and the c-MET antibody MetMab.

The phase II randomized study of ARQ 197 (tivantinib) in NSCLC identified c-MET copy number as a biomarker of ARQ 197 (tivantinib) benefit ([Sequist, Schiller et al, ESMO, 2010](#)).

The phase II randomized study of MetMab (antibody fragment against the c-MET receptor) demonstrated that benefit of MetMab was limited to tumors with c-MET expression using a standardized and centralized IHC methodology ([Spigel et al, ESMO, 2010](#)).

In this study we will evaluate both c-MET copy number and c-MET expression.

3. PATIENT SELECTION

3.1 Eligibility Criteria

Inclusion Criteria:

- 3.1.1 Histologically / cytologically confirmed diagnosis of squamous cell carcinoma of Head and Neck origin not amenable to curative intent therapy. Both HPV(+) and HPV(-) are eligible, but status has to be known prior to randomization (although not required for consenting). Any type of tissue based HPV assessment is acceptable (e.g. p16 IHC or HPV ISH). If local HPV testing is not available slides can be sent to the University of Chicago for HPV testing. Please note that p16 IHC is generally only considered to be accurate for oropharyngeal tumors.
- 3.1.2 Presence of measurable lesions (as per RECIST 1.1). Generally a ≥ 10 mm tumor lesion (in the longest diameter by CT scan) or a Lymph node ≥ 15 mm (short axis) is considered measurable disease when evaluated by CT scan (with a slice thickness no greater than 5 mm). Please review full RECIST 1.1 criteria ([Eisenhauer EA et al, Eur J Ca, 2009](#)) as well as Section 11 for further details.
- 3.1.3 Availability of tissue (10 tumor containing FFPE slides/sections)
- 3.1.4 ECOG performance status of 0, 1 (see Appendix A).
- 3.1.5 Patients who have received cetuximab or another inhibitor of EGFR in the curative intent treatment setting (e.g. with radiation or during induction chemotherapy (prior to definitive, curative intent therapy)) are eligible for the study.
- 3.1.6 Age ≥ 18 years.

Because no dosing or adverse event data are currently available on the use of ARQ 197 (tivantinib) in patients < 18 years of age, children are excluded from this study, but will be eligible for future pediatric trials.

- 3.1.7 Life expectancy of greater than 8 weeks.
- 3.1.8 Patients must have normal organ and marrow function as defined below:

- hemoglobin	≥ 9.0 g/dL
- leukocytes	$\geq 3,000$ /mcL
- absolute neutrophil count	$\geq 1,500$ /mcL
- platelets	$\geq 100,000$ /mcL
- total bilirubin	≤ 1.5 X institutional upper limit of normal
- AST(SGOT)/ALT(SGPT)	≤ 2.5 X institutional upper limit of normal
- serum creatinine	≤ 1.5 X institutional upper limit of normal

OR

– creatinine clearance ≥ 60 mL/min/1.73 m² for patients with creatinine levels above institutional normal.

- 3.1.9 Patients must be able to swallow ARQ 197 (tivantinib) by mouth, unless adequate data about administration by G-tube becomes available. Tablets may be crushed, but must be taken orally.
- 3.1.10 HIV-positive patients with normal immune function (CD4 count >200) are eligible if there are no drug interactions with ARQ 197 (tivantinib) or cetuximab.
- 3.1.11 The effects of ARQ 197 (tivantinib) on the developing human fetus are unknown. For this reason and because tyrosine kinase inhibitors as well as other therapeutic agents used in this trial are known to be teratogenic, women of child-bearing potential and men must agree to use adequate contraception (hormonal or barrier method of birth control; abstinence) prior to study entry and for the duration of study participation. Should a woman become pregnant or suspect she is pregnant while she or her partner is participating in this study, she should inform her treating physician immediately. Men treated or enrolled on this protocol must also agree to use adequate contraception prior to the study, for the duration of study participation, and 4 months after completion of ARQ 197 (tivantinib) administration.
- 3.1.12 Ability to understand and the willingness to sign a written informed consent document.

3.2 Exclusion Criteria

- 3.2.1 Patients who have had chemotherapy or radiotherapy within 2 weeks (6 weeks for nitrosoureas or mitomycin C) prior to entering the study or those who have not recovered from adverse events due to agents administered more than 2 weeks earlier.
- 3.2.2 Nasopharyngeal tumors that show lymphoepithelioma histology
- 3.2.3 Patients who have received more than 2 prior cytotoxic treatments in the palliative treatment setting are ineligible.
- 3.2.4 Patients who have received prior treatment with an EGFR or MET inhibitor in the palliative treatment setting are ineligible
- 3.2.5 Patients with known, active brain metastases should be excluded from this clinical trial because of their poor prognosis and because they often develop progressive neurologic dysfunction that would confound the evaluation of

neurologic and other adverse events. Patients with treated brain metastases stable for ≥ 12 weeks are eligible. Use of corticosteroids (for patients with brain metastasis and other indications for corticosteroid use) is acceptable on a low maintenance or tapering dose schedule.

- 3.2.6 History of allergic reactions attributed to compounds of similar chemical or biologic composition to AR 197 (tivantinib) or cetuximab.
- 3.2.7 Concurrent life-threatening diseases: Patients with diseases which with reasonable certainty do not limit life expectancy to 12 months or less are eligible. Assessment of such concurrent illnesses should be by the Principal Investigator
- 3.2.8 Uncontrolled intercurrent illness including, but not limited to, ongoing or active infection, symptomatic congestive heart failure, unstable angina pectoris, cardiac arrhythmia, or psychiatric illness/social situations that would limit compliance with study requirements.
- 3.2.9 Pregnant women are excluded from this study because ARQ 197 (tivantinib) is a tyrosine kinase inhibitor with the potential for teratogenic or abortifacient effects. Because there is an unknown but potential risk for adverse events in nursing infants secondary to treatment of the mother with ARQ 197 (tivantinib), breastfeeding should be discontinued if the mother is treated with ARQ 197 (tivantinib).
- 3.2.10 Concurrent use of warfarin (therapeutic use) is allowed, but requires close monitoring of PT/INR (See Section 5.2)
- 3.2.11 ARQ 197 (tivantinib) is metabolized by CYP2C19, and to a lesser extent CYP3A4. The metabolism and consequently overall pharmacokinetics of ARQ 197 (tivantinib) could be altered by inhibitors and/or inducers or other substrates of CYP2C19 and CYP3A4. While inhibitors/inducers of these cytochrome P450 isoenzymes are not specifically excluded, investigators should be aware that ARQ 197 (tivantinib) exposure may be altered by the concomitant administration of these drugs.

Because the lists of these agents are constantly changing, it is important to regularly consult a frequently-updated list such as <http://medicine.iupui.edu/clinpharm/ddis/table.aspx>; medical reference texts such as the Physicians' Desk Reference may also provide this information. As part of the enrollment/informed consent procedures, the patient will be counseled on the risk of interactions with other agents, and what to do if new medications need to be prescribed or if the patient is considering a new over-the-counter medicine or herbal product.

- 3.2.12 History of congestive heart failure defined as Class II to IV per New York Heart Association (NYHA) classification; active coronary artery disease (CAD); clinically significant bradycardia or other uncontrolled, cardiac

arrhythmia defined as \geq grade 3 according to National Cancer Institute (NCI) Common Terminology Criteria for Adverse Events (CTCAE), version 4.0, or uncontrolled hypertension; myocardial infarction occurring within 6 months prior to study entry (myocardial infarction occurring >6 months prior to study entry is permitted).

3.2.13 Patients may not be receiving any other investigational agents

3.3 Inclusion of Women and Minorities

Both men and women of all races and ethnic groups are eligible for this trial. Each center will be responsible for ensuring that a representative set of patients (as defined by the Census Bureau) is enrolled.

4. REGISTRATION PROCEDURES

4.1 General Guidelines

Eligible patients will be entered on study centrally at the University of Chicago by the Study Registrar. All sites should call the Study Registrar, , at **[name]** or [contact], to verify agent availability. The UC Phase II Consortium Affiliate Forms are available on the UC P2C website at:

- <https://webres.uccrc.org/login/login>

Except in very unusual circumstances, each participating institution will order DCTD-supplied agents directly from CTEP. Agents may be ordered by a participating site only after the initial IRB approval for the site has been forwarded by the Coordinating Center to the CTEP PIO ([contact]) except for Group studies. Eligible patients will be entered on study centrally at the University of Chicago by the study Registrar. All sites should call the study Registrar at **[name]** to verify agent availability.

ARQ 197 (tivantinib) may be requested by submitting an agent order through PMB Online Agent Order Processing (OAOP) application. Refer to section Section 8.1.3.1 for more information.

Following registration, the study registrar at the University of Chicago will randomize the patient immediately, and patients should begin protocol treatment within 14 days after randomization. Issues that would cause treatment delays should be discussed with the Principal Investigator. If a patient does not receive protocol therapy following registration, the patient's registration on the study may be canceled. The Registrar should be notified of cancellations as soon as possible.

4.2 Registration Process

All patients must be successfully registered and randomized with the University of Chicago Registrar, prior to the commencement of treatment. The following documents should be completed by the research nurse or data manager and faxed to [name] or emailed [contact] to the Registrar:

- Provider of information
- Treating Physician
- Patient name and hospital ID number
- Patient's zip code of residence
- Date & copy of signed informed consent
- Race, gender, date of birth of patient
- Diagnosis and date of initial diagnosis
- HPV status (can be provided later, but is required for successful randomization)
- Complete **Phase II Consortium Affiliate Clinical Trial Patient Registration Form**
- Source documentation for eligibility and pre-study procedures

The research nurse or data manager at the participating site will then call [contact]) or e-mail [contact] to confirm all selection criteria listed in Section 4.0. To complete the registration process, the Coordinator will:

[figure not shown]
- Assign a patient study number
- Register the patient on the study
- Assign patient to treatment arm based on Randomization (see Section 13)
- Fax or e-mail the patient study number and dose to the participating site
- Provide randomization information regarding treatment arm

Call the research nurse or data manager at the participating site and verbally confirm registration.

5. TREATMENT PLAN

Patients are randomized between two arms (see schema below):

1. cetuximab 500mg/m² iv, every two weeks, PLUS ARQ 197 (tivantinib) 360mg BID, by mouth
2. cetuximab 500mg/m² iv, every two weeks

5.1 Agent Administration

Treatment will be administered on an outpatient basis. Reported adverse events and potential risks for ARQ 197 (tivantinib) and cetuximab are described in Section 7. Appropriate dose modifications for ARQ 197 (tivantinib) and cetuximab are described in Section 6. No investigational or commercial agents or therapies other than those described below may be administered with the intent to treat the patient's malignancy.

5.1.1 ARQ 197 (tivantinib) administration

- Patients receive ARQ 197 (tivantinib) on an outpatient basis. The starting dose is 360 mg, by mouth, twice daily.
- The patient will be requested to maintain a medication diary of each dose of medication. The medication diary will be returned to clinic staff at the end of each cycle. A sample medication diary can be requested from the University of Chicago or can be provided by the respective treatment center using a local template.
- ARQ 197 (tivantinib) tablets should be administered orally with meals. A missed or vomited dose (= not taken within 4 hours (i.e. 4 hours before or after) the scheduled time) should not be replaced. The patient should be instructed to take the next scheduled dose at the regularly scheduled time.

5.1.2 Cetuximab administration

- Cetuximab will be given on an outpatient basis every two weeks intravenously at a dose of 500mg/m² (given over 120 minutes the first time, then over 60 minutes subsequently) (all iv).
- It is acceptable to round the cetuximab dose to the nearest hundred if this is the institutional standard practice.
- Patients will receive cetuximab intravenous infusions via infusion pump or gravity drip. The dose of cetuximab is 500 mg/m² and is administered over 120 or 60 minutes. The dose of cetuximab is dependent upon the patient's baseline body weight in kilograms (mg/kg). If there is a $\geq 20\%$ change in body weight from baseline this dose should be recalculated. Patients should be observed closely during cetuximab infusion and for **60 minutes after the infusion**.

Infusion times may be increased for patients who experience mild allergic reactions, but cannot exceed 4 hours. Prior to infusion, the appropriate volume of cetuximab will be drawn from the vial with a sterile syringe and cetuximab will be transferred from the syringe into a sterile evacuated container. Cetuximab will be filtered through a 0.22- μ m protein-sparing or low- protein binding in-line filter. After infusion, 0.9% normal saline will be used to flush the line.

- Premedication with an H₁ antagonist (diphenhydramine 25-50 mg I.V. or oral) 30 minutes prior to infusion should be given for allergic reaction prophylaxis. 50mg should be administered prior to the first dose of cetuximab in an effort to prevent an infusion reaction.
- Four weeks (28 days) constitutes one cycle of treatment. Treatment continues until one of the criteria in Section 5.3 applies.
- If a patient develops a hypersensitivity reaction despite diphenhydramine pretreatment, the infusion should be stopped and observation for 15 to 60 minutes (depending upon the reaction severity) instituted. Infusion reactions to cetuximab may be severe and can occur during or after treatment. At the physician's discretion, it may be possible to resume treatment by administering an H₂ blocker approximately 30 minutes before restarting the infusion. The addition of an H₂ blocker such as famotidine 20 mg IV is optional. If famotidine is unavailable, administer ranitidine 50 mg IV (not cimetidine due to the risk for drug interactions). Re-attempting infusion at a slower rate, possibly over one hour is appropriate. Additional treatment of severe allergic reactions is at the discretion of the treating physician and may include corticosteroids as well as other agents.
- As a routine precaution, patients enrolled in this study will be observed closely for any potential adverse events by the medical staff for the duration of the cetuximab infusion and until at least 1 hour after the end of the initial infusion, in an area with resuscitation equipment and other agents (epinephrine, prednisone equivalents, etc.) available. A nurse must be present in the immediate treatment area throughout the infusion and observation period. A physician must be in close proximity to the patient treatment area. Patients should be instructed to report any delayed reactions to the investigator immediately.
- Details about dose reductions / resumption of therapy on subsequent treatment days are provided in Section 6.

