6. DOSING DELAYS/DOSE MODIFICATIONS

Dose Level	Tivantinib Dose
Starting Dose	360 mg, po, twice a day
-1	240 mg, twice a day
-2	120 mg, twice a day

Up to two dose reductions are acceptable. Persistent toxicities in spite of two dose reductions will result in discontinuation of therapy.

Event Name	Non-hematological toxicities	
Grade of Event	Management/Next Dose for ARQ 197 (tivantinib)	Management/Next Dose for Cetuximab
≤ Grade 1	Continue therapy	Continue therapy. See 6.2
Grade 2	Continue therapy	Continue therapy. See 6.2
Grade 3*	If at least possibly related to ARQ 197 (tivantinib) and not amenable to an established, rapidly effective treatment**: hold ARQ 197 (tivantinib) until resolution to ≤Grade 2	If at least possibly related to cetuximab and not amenable to an established, readily effective treatment**: hold cetuximab until resolution to ≤Grade 2. See 6.2
Grade 4*	If at least possibly related to ARQ 197 (tivantinib) and not amenable to an established, rapidly effective treatment**: hold ARQ 197 (tivantinib) until resolution to ≤Grade 2	If at least possibly related to cetuximab and not amenable to an established, readily effective treatment**: hold cetuximab until resolution to ≤Grade 2. See 6.2
* Treating Physician to assess relatedness and impact on patient health		
** E.g. adverse events that are readily addressed with additional therapy typically within 24 hours – e.g. pain medication for increased pain or insulin for increase blood glucose level.		
Patients requiring a delay of >2 weeks should go off protocol therapy. Patients requiring > two dose reductions should go off protocol therapy.		
Recommended management: For vomiting : antiemetics. For diarrhea : Loperamide antidiarrheal therapy. Dosage schedule: 4 mg first onset, followed by 2 mg with each loose motion until diarrhea-free for 12 hours (maximum dosage: 16 mg/24 hours). Adjunct anti-diarrheal therapy is permitted and should be recorded when used.		

Event Name	Hematological Toxicities***
------------	-----------------------------

Grade of Event	Management/Next Dose for ARQ 197 (tivantinib)	Management/Next Dose for Cetuximab
Grade 1	No change in dose	No change in dose
Grade 2	No change in dose	No change in dose

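### Section 5.1.2 allows cetuximab to be restarted after an infusion reaction with no grade limit, while Section 6.2 bars any further cetuximab after grade 3 or 4

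*Combined protocol and SAP*

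**What the plan says.** Section 5.1.2 (Cetuximab administration) covers a hypersensitivity reaction that occurs despite diphenhydramine. The infusion is stopped and the patient is observed for 15 to 60 minutes, with severity deciding only how long. The bullet then warns: "Infusion reactions to cetuximab may be severe and can occur during or after treatment". Restart is left to the treating doctor's judgment, in wording that names no grade: "it may be possible to resume treatment by administering an" (the agent meant is an H2 blocker, given roughly half an hour before the restart). On the rate it says: "Re-attempting infusion at a slower rate, possibly over one hour is appropriate".

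The closing bullet of 5.1.2 says that details on "resumption of therapy on subsequent treatment days are provided in Section 6". Two other pointers are not limited by day. Section 5.1 states: "Appropriate dose modifications for ARQ 197 (tivantinib) and cetuximab are described in Section 6". The non-hematological table in Section 6 sends every grade to 6.2; the entry for grades up to 2 reads "Continue therapy. See 6.2".

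Section 6.2 grades the same event:
- Grade 1: halve the rate and watch closely.
- Grade 2: stop, treat, then restart at half rate.
- Grade 1 or 2 in general: the rate reduction is permanent. A reaction that is only a delayed drug fever is exempt and keeps its dose and rate.
- Grade 3 or 4: stop at once, disconnect the line, and give no more cetuximab. A further bullet repeats this as permanent discontinuation for severe reactions.

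**The concern.** Two sections instruct staff on the same bedside event. Section 5.1.2 permits something that 6.2 forbids, and its own cross-reference hands only later treatment days to Section 6. Someone at the infusion chair could reasonably conclude that the same-day decision belongs to 5.1.2.

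The patients at issue are those with the most serious reactions. Section 6.2 places bronchospasm needing parenteral medication, angioedema and hypotension in grade 3, and anaphylaxis in grade 4. What is at stake is rechallenge of such a patient within the same session. Both arms receive cetuximab, so the instruction reaches every treated patient.

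The restart rate is a lesser matter. Section 5.1.2 gives a loose description where 6.2 gives a number.

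**Working it through.** **Step 1: grade by grade**

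| Reaction | Section 5.1.2 | Section 6.2 | Result |
|---|---|---|---|
| Grade 1, during infusion | Stop, observe, may restart slower | Halve the rate; no stop required | Differ on stopping |
| Grade 2, during infusion | Stop, observe, may restart slower | Stop, treat, restart at half rate | Agree if the physician chooses half rate |
| Grade 1 or 2, delayed drug fever only | No restart arises; fever follows the infusion | Dose and rate unchanged | No conflict |
| Grade 3 or 4 | Same text, so restart at discretion | Disconnect; no further cetuximab | 5.1.2 permits what 6.2 forbids |

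The grade 3 or 4 row is the substance of the point.

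**Step 2: is the restart in 5.1.2 a same-day restart?** The section does not say so in those words. Three features imply it: an observation period of 15 to 60 minutes, an H2 blocker about 30 minutes before restarting, and the separate bullet for later treatment days.

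**Step 3: the rate.** Planned times in 5.1.2 are "given over 120 minutes the first time, then over 60 minutes subsequently". Let D be the full dose and f the fraction left at the reaction. Assume a constant planned rate beforehand, and the remaining dose given over exactly 60 minutes. The restart rate is then fD/60.

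- First infusion: planned rate D/120, half rate D/240.
  - Restart ÷ planned = (fD/60) ÷ (D/120) = 2f, so it is slower than planned only if f < 0.5.
  - Restart ÷ half rate = (fD/60) ÷ (D/240) = 4f, so it is at or below half rate only if f ≤ 0.25.
  - Example, minute 75: f = 1 − 75/120 = 0.375, and 4f = 1.5. Half rate would take 240 × 0.375 = 90 minutes.
- Later infusion: planned rate D/60, half rate D/120.
  - Restart ÷ planned = f, so it is slower than planned whenever some dose has been given.
  - Restart ÷ half rate = 2f, so it is at or below half rate only if f ≤ 0.5.
  - Example, minute 15: f = 1 − 15/60 = 0.75, and 2f = 1.5. Half rate would take 120 × 0.75 = 90 minutes.

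Under those assumptions, a one-hour restart can count as slower in the sense of 5.1.2 and still exceed the rate in 6.2.

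**The case against.** The strongest reply is that the sections can be reconciled. Section 5.1.2 is permissive and general, while 6.2 is graded, categorical and not limited by day. A physician who uses the discretion only where 6.2 allows it complies with both, and Section 5.1 and the Section 6 table both lead there. This stands as a reason to expect little harm in practice. It does not withdraw the permission in 5.1.2, and nothing states that 6.2 prevails for the same session.

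It can also be said that 5.1.2 has its own severity limit: "Infusion times may be increased for patients who experience mild allergic reactions, but cannot exceed 4 hours". That sentence limits who may have a longer infusion. It places no condition on restarting. The last sentence of the restart bullet, on additional treatment of severe allergic reactions, does not exclude those patients from restart either.

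On the rate, the objection largely succeeds. A reader might infer that 5.1.2 prescribes a rate that contradicts 6.2 over definite minutes of the infusion. The documents do not support that. A half-rate restart is a slower rate and satisfies both sections at any minute. The one-hour wording is only a suggestion and could also mean more than an hour. The multiples in Step 3 hold only under the exact 60-minute, remaining-dose reading. What survives is that 5.1.2 omits the 50% figure and offers an example that can miss it.

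**Conclusion.** The grade conflict is real and lies in current text: 5.1.2 allows a discretionary restart after a reaction of any grade, and 6.2 rules it out after grade 3 or 4. The restart rate is imprecise wording, not a second contradiction.

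Severity is minor. Harm requires a site to act on 5.1.2 without 6.2, and the reading as a same-day restart is an inference, though a strong one. The documents give no rate of infusion reactions by grade for this population, so no patient count is claimed.

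Three further readings would go too far. The protocol does not direct rechallenge after grade 3 or 4; it fails to exclude it in one place. Section 6.2 does not halve the rate after every grade 1 or 2 reaction, since isolated delayed drug fever is exempt. And nothing here touches the sample size, power or analysis in Section 13.

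**What to change.** In the restart bullet of Section 5.1.2, delete the suggestion of one hour and add:

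*Resumption is allowed only after a grade 1 or 2 reaction, at 50% of the previous rate, per Section 6.2. No further cetuximab is given after a grade 3 or 4 reaction. Section 6.2 governs same-day restart as well as later infusions.*

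Also state whether a grade 1 reaction requires stopping, as 5.1.2 has it, or only slowing, as 6.2 has it. That is a clinical choice for the sponsor.

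Leave the 4-hour limit where it is and do not repeat it in the new text. A full first dose at half rate takes 120 ÷ 0.5 = 240 minutes, exactly 4 hours, and 5.1.2 does not say whether an observation pause counts. Repeating the limit beside the restart rule would import that ambiguity.

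The cost is three sentences and one clarification. The 6.2 rules for grades 2 to 4 and for delayed drug fever stay as they are, and no visits, procedures or patients are added.
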